 - Induce clinical remission based on a total Mayo Clinic score (i.e., score of ≤ 2) and subscores (i.e., no subscores > 1).
 - To characterize the PK of KHK4083 in subjects with moderately active UC following multiple dose administration;
 - To evaluate the development of antibodies against KHK4083 (immunogenicity).
- Refer to Section 10.2 for additional details on all secondary endpoints.

Exploratory:

- To determine if multiple doses of KHK4083 administered during the Open-label Extension (OLE) / Long-term Extension (LTE) Therapy phase will meet the following objectives at Week 52 (or as noted) when compared with Baseline (Week 0) scores (or subscores) or assessments:
 - Improve clinical signs and symptoms based on total Mayo Clinic score;
 - Improve clinical signs and symptoms based on partial Mayo Clinic scores (excludes endoscopy subscores) at Week 16 through Week 52, and the LTE Therapy Follow-up Period (Week 56 through Week 64);
 - Induce a clinical response based on a reduction in the total Mayo Clinic score and rectal bleeding subscale (or a defined absolute rectal bleeding score);
 - Induce clinical remission based on a total Mayo Clinic score and subscores;
 - Induce durable clinical responses and durable clinical remissions (present at both Weeks 12 and 52), and glucocorticoid-free clinical remission;
 - Induce mucosal healing based on the mMES;
 - Improve the mucosa based on the mMES, UCEIS, and/or modified Baron endoscopic score;

- Induce remission (Week 12; Week 52) based on modified Mayo endoscopy, stool frequency, and rectal bleeding subscores (defined as an mMES of 0 or 1, stool frequency subscore of 0 or 1, and rectal bleeding subscore of 0);
- To evaluate the activity of KHK4083 on health-related quality of life (HRQL), which will be based on the subject's completed Inflammatory Bowel Disease Questionnaires (IBDQs) in comparison to Baseline assessments;
- To measure changes from Baseline in corticosteroid (glucocorticoid) dosages;
- To determine the percentage of subjects who are glucocorticoid-free from Week 16 through Week 52, and through the OLE/LTE Therapy Follow-up Period (Week 56 through Week 64);
- To evaluate the pharmacodynamic (PD) profile of KHK4083;
- To explore the PK-PD relationships.

Refer to Section 10.3 for additional details on exploratory endpoints.

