7.2 Inclusion Criteria

Subjects may be included in the study if they meet all of the following Inclusion Criteria:

- 1) Subject is able and willing to comply with study procedures, and to adhere to dosing and visit schedules and follow-up procedures as described in the protocol and ICF;
- 2) Subject voluntarily signs/dates an Institutional Review Board (IRB)/Independent Ethics Committee (IEC)-approved ICF in accordance with regulatory and institutional guidelines;
Note: Written informed consent must be obtained prior to performing any study-related procedure.
- 3) Male and female subjects ≥ 18 years of age at the time of enrollment;
- 4) Subject has UC that was diagnosed at least 6 months prior to the Screening visit;
- 5) Subject has moderately active UC, defined as:
 - a) Total Mayo Clinic score of 4 to 9 (range: 0 to 12, with higher scores indicating more disease activity);
 - b) Endoscopy subscore (mMES determined by a central reader) of at least 2; and
 - c) Disease that extends ≥ 15 cm from the anal verge.
- 6) Subject has had previous treatment (within 5 years prior to Screening) with one or more of the following: corticosteroids, immunosuppressive medications or TNF antagonist therapy that was unsuccessful because of a lack of efficacy response or AEs, as defined below:
 - a) corticosteroids for induction therapy of at least prednisolone-equivalent of 20 mg (or oral budesonide 9 mg) oral daily for 2 weeks or injectable for 1 week, or for maintenance therapy at least two failed attempts to reduce to less than prednisolone-equivalent 10 mg (or oral budesonide 3 mg) oral daily, or a history of intolerance to corticosteroids (including but not limited to hypertension, insomnia, osteopenia, osteoporosis, hyperglycemia, infection or Cushing's syndrome);
 - b) Azathioprine or 6-mercaptopurine of at least 1.5 mg/kg/day or 0.75 mg/kg/day, respectively, for 8 weeks, or a history of intolerance to either agent (including but not limited to nausea, vomiting, abdominal pain, aspartate aminotransferase (AST) or alanine aminotransferase (ALT) elevations, thiopurine methyltransferase genetic mutation, or infection);

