7.3 Exclusion Criteria

Subjects must be excluded from participating in this study if they meet any of the following Exclusion Criteria:

- 1) Subject, who, for any reason, is judged by the Investigator to be inappropriate for this study, including a subject who is unable to communicate or cooperate with the Investigator, who has/had a psychiatric illness, disability or social situation that may compromise the safety of the subject during the study or affect the ability of the subject to adhere to study procedures;
- 2) Subject has a medical history of clinically significant (as determined by the Investigator or the Sponsor) cardiac, renal, hepatic/biliary (e.g., sclerosing cholangitis), pulmonary, or other medical conditions or is not generally in good health.

Subjects with the history of immunologic, autoimmune or chronic inflammatory disorders (e.g., uveitis, rheumatoid arthritis, ankylosing spondylitis or spondyloarthritis, psoriasis) other than UC or autoimmune connective tissue diseases (e.g., systemic lupus erythematosus, systemic sclerosis) and are well controlled may be included into the trial after consultancy with medical monitor. Subjects with thyroid disorders, vitiligo, and alopecia are eligible for inclusion.

- 3) Subject's UC had failed to respond to:
 - a) Two or more biologic treatments with different mechanisms of action (e.g., infliximab, vedolizumab and golimumab), or
 - b) Three or more anti-TNF biologics, e.g., infliximab, adalimumab;
- 4) Subject requires prescription treatment for UC, except for the stable, oral treatment of UC as follows:
 - a) Aminosalicylates (5-ASA acid or mesalamine ≤ 4.8 g/day; sulfasalazine ≤ 3 g/day) for at least 14 days prior to the Screening visit; and/or
 - b) Glucocorticoids (≤ 20 mg/day prednisolone or the equivalent, or budesonide ≤ 9 mg/day) for at least 14 days prior to the Screening visit (or for 4 weeks if a course of corticosteroids had started at less than 8 weeks prior to Screening visit); and/or
 - c) Azathioprine up to 3 mg/kg/day or 6-mercaptopurine up to 1.5 mg/kg/day for a total treatment period of at least 12 weeks, including 4 weeks of stable treatment, prior to the Screening visit.
- 5) Subject has received any of the following prior treatments or treatments within the specified time:

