10.3 Exploratory Endpoints

Efficacy and PD exploratory endpoints will be included in this study for all subjects with moderately active UC who receive both Induction Therapy and OLE/LTE Maintenance Therapy. The exploratory endpoints for all subjects who receive both Induction Therapy and OLE/LTE Maintenance Therapy are as follows:

- Clinical improvement at Week 52;
Improvement will be based on a reduction (mean change from Baseline [Week 0] to Week 52) in the total Mayo Clinic score (0 to 12).
- Clinical improvement at Weeks 16, 20, 24, 28, 32, 36, 40, 44, 48, and 52 and at OLE/LTE Therapy Follow-up Period visits (Weeks 56, 60, and 64);
Improvement will be based on mean changes from Baseline (Week 0) in the partial (excludes endoscopy subscores) Mayo Clinic score (0 to 10).

- Clinical response at Week 52;
A clinical response is defined as a reduction in the total Mayo Clinic score of at least 3 points and a decrease of at least 30% from Baseline (Week 0) to Week 52, and a reduction in the rectal bleeding subscale of at least 1 point from Baseline (Week 0) to Week 52 or an absolute rectal bleeding score of 0 or 1 at Week 52.
- Clinical remission (i.e., a total Mayo Clinic score of ≤ 2 and no subscores > 1) at Week 52;
- Durable clinical responses and durable clinical remissions at Week 52 (i.e., present at both Week 12 and Week 52), and glucocorticoid-free clinical remission at Week 52;
- Mucosal healing (i.e., an mMES of 0 or 1) at Week 52;
- Improvement in the mucosa according to the following assessments:
 - At least a 1-point improvement in the mMES from Baseline (Week 0) to Week 52;
 - A mean change in the UCEIS score from Baseline (Week 0) to Week 52; and/or
 - At least a 1-point improvement in the modified Baron endoscopic score from Baseline (Week 0) to Week 52.
- Remission (i.e., mMES of 0 or 1, stool frequency subscore of 0 or 1, and rectal bleeding subscore of 0) rates at Week 12 and Week 52;
- Improvement in the HRQL, which will be based on the subject's completed IBDQs;
- Lowered corticosteroid (glucocorticoid) dosages;
- Glucocorticoid-free treatment duration from Week 16 through Week 52, and through the OLE/LTE Therapy Follow-up Period (Week 56 through Week 64);
- PD profile of KHK4083;
- PK-PD relationships.

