 - Glucocorticoid-free clinical remission at Week 52 will be defined in the case that clinical remission is present at Week 52 and no glucocorticoid listed in Section 9.3 is used from Week 16 through Week 52.
- Glucocorticoid dosages:
 - Baseline glucocorticoid dosages (times) will be defined as the total number of administrations of glucocorticoid listed in Section 9.3 that is used during Double-Blind Induction Period (from Day 1 to a day before Week 16). For the subject who receives no glucocorticoid, the dosages will be 0.

	Forms			
	Title	Statistical Analysis Plan Template		
	Code	Version	Effective Date	Page
	FRM_ST03_032	01	23 Apr 2015	32 of 53

- Glucocorticoid dosages (times) at Week 16 through Week 52 will be defined as the total number of administrations of glucocorticoid listed in Section 9.3 that is used during OLE/LTE Therapy Period (from Week 16 to Week 52). For the subject who receive no glucocorticoid, the dosages will be 0.
- Glucocorticoid dosages (times) at Week 16 through LTE Therapy Follow-up Period will be defined as the total number of administrations of glucocorticoid listed in Section 9.3 that is used during LTE Therapy Period and LTE Therapy Follow-up Period (from Week 16 to Follow-up 3). For the subject who receives no glucocorticoid, the dosages will be 0.
- Glucocorticoid dosages (times) at Week 16 through OLE Therapy Follow-up Period will be defined as the total number of administrations of glucocorticoid listed in Section 9.3 that is used during OLE Therapy Period and OLE Therapy Follow-up Period (from Week 16 to Follow-up 3). For the subject who receives no glucocorticoid, the dosages will be 0.
- If there is glucocorticoid that the number of administrations is unknown, it will be assumed that the glucocorticoid was used at a frequency of an administration per day.
- For the subjects who do not move to OLE/LTE Therapy Period, “Glucocorticoid dosages (times) at Week 16 through Week 52” and “Glucocorticoid dosages (times) at Week 16 through OLE/LTE Therapy Follow-up Period” will not be defined.
- Change from baseline in corticosteroid (glucocorticoid) dosages will be defined as follows:
 - Change from baseline in corticosteroid (glucocorticoid) dosages at Week 16 through Week 52 = Glucocorticoid dosages at Week 16 through Week 52 - Baseline glucocorticoid dosages

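### The SAP's steroid-sparing outputs pool subjects on no glucocorticoid at entry, which dilutes any effect by the unstated share of entry users, and SAP 9.3 may leave out the entry steroids themselves

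*Protocol*

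**What the plan says.** Protocol 5 lists "To measure changes from Baseline in corticosteroid (glucocorticoid) dosages" and "To determine the percentage of subjects who are glucocorticoid-free from Week 16 through Week 52" among the exploratory objectives. Protocol 10.3 turns the first into the endpoint "Lowered corticosteroid (glucocorticoid) dosages" and adds glucocorticoid-free duration and glucocorticoid-free clinical remission. The population is everyone who goes on to the extension: "The exploratory endpoints for all subjects who receive both Induction Therapy and OLE/LTE Maintenance Therapy are as follows".

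Nothing requires a subject to be on a steroid at entry. Exclusion criterion 4 in Protocol 7.3 allows stable background treatment from three classes joined by and/or, one of which is "Glucocorticoids (≤ 20 mg/day prednisolone or the equivalent, or budesonide ≤ 9 mg/day) for at least 14 days prior to the Screening visit". Inclusion criterion 6 in Protocol 7.2 concerns treatment history only: "Subject has had previous treatment (within 5 years prior to Screening) with one or more of the following".

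SAP 7.3 defines dosage as a number of administrations. The baseline count runs from Day 1 to the day before Week 16, and the later count from Week 16 to Week 52 or to the last follow-up visit. For non-users the rule is: "For the subject who receives no glucocorticoid, the dosages will be 0". Glucocorticoid-free remission at Week 52 needs clinical remission and that "no glucocorticoid listed in Section 9.3 is used from Week 16 through Week 52". SAP 9.3 then limits what is a glucocorticoid for these outputs to concomitant medications with ATC code H02AB whose administration began from Day 1. SAP 4.4 bases percentages on the whole treatment or cohort group. Tables 14.2-3.5.1 to 14.2-3.5.4 cover dosages and duration, with no split by Week 0 use.

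**The concern.** The question behind these endpoints is whether KHK4083 lets subjects on steroids reduce or stop them. Only subjects on a steroid at Week 0 can answer it. As planned, they are mixed with subjects who have nothing to reduce, who contribute zeros to the dosage change and steroid-free status by default.

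The entry mix can also differ by chance between arms, since Part A has 9 active subjects per dose and cohorts are enrolled one after another. A difference between doses in these outputs could then reflect who entered on steroids. The literal wording of SAP 9.3 adds a separate problem: a steroid that had to be stable before Screening did not begin on or after Day 1, so the entry users may be counted as non-users too.

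**Working it through.** **Plan's own figures.** The documents state no glucocorticoid rate, weaning effect or share of entry users. The only figures to reproduce are the sample sizes: 51 / (1 − 0.15) = 60 randomized; recommended dose 9 + 18 = 27; placebo 3 × 3 + 6 = 15. All agree with Protocol 12.3.4.

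**Assumed inputs.** p = share on a daily glucocorticoid at entry; w = share of those users off it by Week 16; r = share of entry non-users given a steroid later (rescue is allowed after Week 12, Protocol 8.5).

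**Case 1: SAP 9.3 read literally.** Entry steroids are not counted. A user who stays on the same steroid throughout has a count of 0 in both windows and meets the steroid condition for glucocorticoid-free remission. If nobody starts a new steroid, 100% meet that condition at every p, whether or not anyone was weaned.

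**Case 2: entry steroids counted whenever started.**

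- Share steroid-free = p × w + (1 − p) × (1 − r).
- Between two arms with the same p and r, the difference is p × (difference in w). For w = 50% against 25% it is 25 points × p. In entry users alone it stays 25 points.
- Windows: Day 1 to Day 112 is 112 days; Week 16 (Day 113) to Week 52 (Day 365) is 365 − 113 + 1 = 253 days.
- A daily user who changes nothing scores 253 − 112 = +141. A daily user who stops at Week 20 scores 28 − 112 = −84.
- With r = 0, the all-subject mean change is p × (change in users).

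| p (assumed) | Steroid-free with no weaning, r = 0 | Same, r = 20% | 25-point difference appears as | Mean change, users unchanged | Mean change, all users off at Week 20 | Users among 27 / 15 |
|---|---|---|---|---|---|---|
| 30% | 70% | 56% | 7.5 points | +42 | −25 | 8.1 / 4.5 |
| 50% | 50% | 40% | 12.5 points | +71 | −42 | 13.5 / 7.5 |
| 70% | 30% | 24% | 17.5 points | +99 | −59 | 18.9 / 10.5 |

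The last column is before any loss between induction and the extension.

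**Glucocorticoid-free remission.** If remission is independent of entry use and nobody is weaned, the rate is remission × (1 − p). At p = 50% and remission of 10% to 30% this gives 5% to 15%. It cannot exceed the remission rate.

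**Duration.** The SAP 7.3 formula subtracts the Week 16 date from the date of the first later glucocorticoid. It gives no value for a subject who never takes one.

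**The case against.** The strongest reply is that little rests on these outputs. They are exploratory, and Protocol 12.3.5 disclaims Type I error control. SAP 7.3 names UCEIS, total Mayo and partial Mayo for its Week 52 ANCOVA, not steroid dosage, although Protocol 12.3.3 speaks more broadly of all continuous exploratory variables. Taper is at the investigator's discretion. In the open-label extension, subjects randomized to placebo receive KHK4083 (SAP Table 2, note 3), so a user-only row would not isolate steroid sparing against an untreated group there. Medications are also listed by subject, so entry use can be examined. All of this stands and limits the consequence. It does not make the planned summaries answer the stated objective.

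A reader might infer that the glucocorticoid-free rates will be high whatever KHK4083 does. The documents do not support that. The entry share is not given: with no weaning and r = 0, the floor runs from 90% at p = 10% to 10% at p = 90%. Non-users can lose steroid-free status through rescue after Week 12, so keeping it may reflect disease control. Glucocorticoid-free remission is capped by remission. The SAP table list also has no table titled for the plain glucocorticoid-free percentage.

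A reader might also infer that the mean dosage change is simply pulled toward a no-effect value of zero. It is not. If entry steroids are counted, the unequal windows put the no-effect value for a daily user at about +141, so dilution acts on a measure that is already off-centre.

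**Conclusion.** The point holds in limited form. Entry use is optional, the steroid outputs cover all extension subjects with zeros for non-users, and none is restricted to or split by Week 0 use. Any steroid-sparing effect is diluted by the factor p: 25 points becomes 7.5, 12.5 or 17.5 at assumed p of 30%, 50% or 70%. Those figures assume equal p and r across arms and that entry steroids are counted. If SAP 9.3 is applied as worded, entry steroids are not counted at all, and the outputs reflect new starts after Day 1 rather than weaning. On either reading, the planned outputs cannot show whether entry users came off steroids. The effect is confined to the exploratory steroid-sparing interpretation; the primary and secondary efficacy results are untouched.

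**What to change.** Three changes to the SAP, which only work together:

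1. In SAP 9.3, count H02AB medications ongoing at Day 1 as well as those started later. Without this, restricting to entry users selects the very subjects whose steroid is ignored.
2. In SAP 7.3 and Tables 14.2-3.5.1 to 14.2-3.5.4, and for glucocorticoid-free remission, report results in subjects on a glucocorticoid at Week 0, with n by arm, as the steroid-sparing result. Keep the all-subject result as a second row. State the duration value for a subject with no glucocorticoid after Week 16.
3. Express the dosage change per day over comparable periods against Week 0 use, replacing the 112-day and 253-day administration counts.

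The cost is SAP wording, one subgroup flag and reprogramming of the dosage derivation. Prior and concomitant medication is already collected, so no new data are needed. The drawback is few subjects per arm: about 8 and 4.5 of the planned 27 and 15 at p = 30%, before extension losses. The subset should therefore be presented descriptively.

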6 STUDY DESIGN

6.1 Overall Study Design and Plan

This Phase 2, double-blind clinical study of multiple ascending doses of KHK4083 (or placebo) with an OLE Therapy phase will be conducted in approximately 60 randomized adult subjects with moderately active UC who have a documented unsuccessful previous treatment. The study design was revised to convert the post induction phase of the study from a LTE to an OLE.

Male and female subjects ≥ 18 years of age with moderately active UC, defined as a total Mayo Clinic score of 4 to 9 (range: 0 - 12, with higher scores indicating more active disease) with an mMES of at least 2 as determined by a central reader, and disease that extends ≥ 15 cm from the anal verge are eligible to participate in this study.

This multicenter study will be conducted at approximately 40 investigative sites in the US, Russia, Hungary, Poland, Romania, Serbia, and Czech Republic; other countries may be included as needed. The study will include a 4-week Screening Period, followed by a total of up to 64 weeks (treatment and follow-up) on study from the time of randomization to study completion.

[figure not shown]
The Treatment Period includes double-blind Induction Therapy (12 weeks) and OLE Therapy (40 weeks) for eligible subjects at Week 12. Subjects already enrolled in the double-blind, LTE under preceding versions of the protocol who worsen may be eligible to transition to the OLE up to Week 28. Selected Kyowa Kirin Pharmaceutical Development, Inc. (hereinafter

referred to as the Sponsor) personnel will be unblinded after the last subject completes Induction Therapy (refer to Section 8.4 for details).

Post-treatment assessments will continue for 16 weeks after the last infusion associated with the subject's treatment period. The on-site follow-up visits will be at Weeks 16, 20, and 26 for subjects who only receive Induction Therapy or at Weeks 56, 60, and 64 for subjects who receive both Induction and OLE/LTE Therapies. The date of the subject's last post-treatment study visit will be considered the End-of-Study date.

The Study design is displayed in Figure 6.1-1.

Figure 6.1-1 Study Design Diagram

Non-completer (NC) - Subject did not complete Induction Therapy

- a: **For those subjects who enrolled under Amendment #1-** Subjects will be in the study for a total of up to 64 weeks. The double blind treatment period includes Induction Therapy (12 weeks) and LTE therapy (40 weeks). A post treatment follow-up period will be conducted at either Weeks 16, 20 and 26 for subjects who only receive Induction Therapy or at weeks 56, 60 and 64 for subjects who receive both induction and LTE Therapies
- b: Cohort 4 will receive the recommended dose (1.0, 3.0, or 10 mg/kg) determined from safety assessments of Cohorts 1 - 3 in Part A.
- c: Endoscopic Responders (ER) include subjects who met the criteria for clinical response at Week 12 and non-responders (NR) includes subjects who did not meet the criteria of a clinical response at Week 12.
- d: **For those subjects who enroll under Amendment #2-**All subjects who complete the induction period, i.e., (received at least of 5 of the 6 doses of double-blind therapy and have Week 12 sigmoidoscopy results from the central reader) and are eligible to continue on in the study have the option to enter the OLE therapy part of the trial and receive 10 additional treatments of KHK4083 once every 4 weeks from week 12 through week 48 at the same dose used in the cohort that they were enrolled in.

C=cohort; IV=intravenous; LTE=long-term extension; OLE=Open-label Extension; MAD=multiple ascending dose; R=randomization.

6.1.1 Induction Therapy: Week 0 to Week 12 (Last Dose at Week 10)

Double-blind Induction Therapy is separated into Part A for administration of multiple ascending IV doses of KHK4083 (or placebo) to subjects in Cohorts 1 - 3 and Part B for administration of the recommended IV dose (one of three dose levels identified in Part A) of KHK4083 (or placebo) to subjects in Cohort 4. Subjects in Part A are prohibited from participating in Part B.

Subjects in each cohort will be randomly assigned in a 3:1 ratio to receive KHK4083 or placebo by IV infusion over 60 minutes (\pm 10 minutes). Each subject will receive a total of 6 treatments (one IV infusion per treatment) every 2 weeks from Week 0 (Day 1) to Week 10 of Induction Therapy. Safety assessments (e.g., after 2 treatments for 1.0 mg/kg and 3 treatments for 3.0 and 10 mg/kg are administered and 14-day safety data from the last treatment are available) will determine whether dosing will continue for subjects within a cohort and if the investigational product will be administered at the next higher dose level for subjects in the next cohort in Part A or for Cohort 4 in Part B (refer to Section 6.3 for details on the Safety Monitoring Plan).

For subjects in all cohorts, a sigmoidoscopy with biopsy is scheduled at Week 12 to assess improvement in the mucosa from Baseline (Week 0) to Week 12. It is highly recommended that the sigmoidoscopy with biopsy be performed within 7 to 13 days prior to the Week 12 visit. The sigmoidoscopy results from the central reader are required before a subject receives treatment in the OLE/LTE Therapy phase.

6.1.2 Long-term Extension Therapy: Week 12 (First Dose) to Week 52

The LTE is only active for subjects who entered it prior to approval of Amendment 2. Subjects who sign an ICF under Amendment 2 are eligible for the OLE (see Section 6.1.3).

Subjects who completed double-blind Induction Therapy (i.e., at least five of six treatments) and had a clinical response or mucosal healing were eligible to continue in double-blind LTE Therapy. A clinical response is defined as a reduction in the total Mayo Clinic score of at least 3 points and a decrease of at least 30% from Baseline (Week 0) to Week 12, and a reduction in the rectal bleeding subscale of at least 1 point from Baseline (Week 0) to Week 12 or an absolute rectal bleeding score of 0 or 1 at Week 12. Mucosal healing is defined as a mMES of 0 or 1.

All subjects who qualified were to have been given two options:

- 1) To receive no further treatment and proceed directly to the Induction Therapy Follow-up Period (Week 16 through Week 26); or
- 2) To continue in double-blind LTE Therapy and receive 10 additional treatments of KHK4083 (at the same dose administered to that subject during Induction Therapy) or placebo as maintenance therapy. Each subject will receive one IV infusion every 4 weeks from Week 12 to Week 48 followed by an End-of-LTE Therapy visit at Week 52, and then proceed to the LTE Therapy Follow-up Period (Week 56 through Week 64). Refer to Section 8.1.4.2 for additional dosing details in LTE Therapy.

Note: Subjects who already started treatment in the double-blind LTE Therapy will continue to receive KHK4083 or placebo during LTE Therapy. If their UC worsens or flares up to Week 28, they may transition to OLE therapy.

Subjects who did not qualify were to have received no further treatment and entered the Induction Therapy Follow-up Period.

6.1.3 Open-label Extension Therapy: Week 12 (First Dose) to Week 52

Subjects who complete double-blind Induction Therapy (i.e., at least five of six treatments) are eligible to enter OLE Therapy (refer to Section 7.4 for specific eligibility criteria).

All subjects who qualify will be given two options:

- 1) To receive no further treatment and proceed directly to the Induction Therapy Follow-up Period (Week 16 through Week 26); or
- 2) To receive 10 treatments of open-label KHK4083 (at the same dose administered to that subject during Induction Therapy) as maintenance therapy. Each subject will receive one IV infusion every 4 weeks from Week 12 to Week 48 followed by an End-of-OLE Therapy visit at Week 52, and then proceed to the OLE Therapy Follow-up Period (Week 56 through Week 64). Refer to Section 8.1.4.2 for additional dosing details in OLE Therapy.

